#### *Quantitative Safety Measures*

1. bigonial width (mm)
2. cortical thickness under the insertion point of the masseter muscle at the mandibular ramus (mm) (left and right)
3. mandibular flare angle (degrees; left and right)
4. gonial angle (degrees; left and right)

#### *Qualitative Safety Measures*

1. mandibular condylar head shape (A-L)
2. mandibular condylar cortical surface (Yes or No)
3. mandibular condylar head (Regular, Thin, Thick)
4. mandibular condylar position (A-J)
5. glenoid fossa and articular eminence (Yes or No)

CT scan is only done at screening (baseline), treatment cycle 1 day 90 and the exit visit. For the CT safety measurements, the exit visit will be displayed as treatment cycle 1 exit visit and treatment cycle 2 exit visit. Only subjects who received the second injection will be included in the treatment cycle 2 exit visit. Subjects who received only 1 treatment will be included in the treatment cycle 1 exit visit.

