The present study includes CT and dental examinations developed by Allergan with input from consultants and specifically designed to identify potential effects of BOTOX treatment of MMH on the mandible and teeth. The CT scan captured by a CT technologist will be transferred to a central reader, who will review it to assess for changes in lower facial shape (masseter muscle volume, bigonial width, mandibular flare angle, and gonial angle) as well as relevant indicators of change in bone structure (mandibular condylar head shape, mandibular condylar cortical surface, mandibular condylar head, mandibular condylar position, glenoid fossa/eminence, and cortical thickness under the insertion point of the masseter muscle at the mandibular ramus). The dental examination will be conducted by a dentist to assess for any potential changes in dentition, occlusion, and overall oral health (Attachment 12.1.7). Both CT and dental measures will be taken at screening (considered as baseline), day 90, and at study exit (day 360 or study discontinuation).

In summary, the data obtained from this study will be used to develop a better understanding of the safety and efficacy of different dose regimens of BOTOX for the treatment of MMH.

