#### 5.10 Retreatment

[figure not shown]
After treatment on day 1, subjects will receive a second treatment based on meeting the following criteria at the day 180 visit:

- Allergan decision and written notification to study sites allowing a second treatment
- Subject has presence of bilateral masseter muscle hypertrophy of at least marked (grade 4), as measured by the investigator using the MMPS.
- Females of childbearing potential must have a negative urine pregnancy test prior to treatment.

The second treatment is only allowed at the day 180 visit. Retreatment is prepared and administered in the same manner as described in Sections 5.1 to 5.9. Subjects will receive the same treatment at day 180 as they received at day 1.

- **6** Response Measures and Summary of Data Collection Methods
- **6.1** Efficacy Measures
- 6.2 Primary Efficacy Measure
- lower facial volume (cm³) calculated from VECTRA M3 digital photography system 3D image models (see Attachment 12.1.2)
- 6.3 Secondary Efficacy Measure
- investigator's assessment of MMH using the MMPS (5 grades: 1 = minimal, 2 = mild, 3 = moderate, 4 = marked, 5 = very marked; see Attachment 12.1.1)

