## 8.8 Early Discontinuation of Subjects

Subjects may voluntarily withdraw from the study at any time. Notification of early subject discontinuation from the study and the reason for discontinuation will be made to Allergan and will be clearly documented on the appropriate case report form. All day 360/study exit procedures should be performed (Table 1), including an exit CT scan, unless the investigator proposes a medical reason to waive the exit CT scan.

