### 1.1 Primary Study Objectives and Design

The objectives of this study are to evaluate the safety and efficacy of a range of doses of BOTOX for the treatment of subjects with bilateral masseter muscle hypertrophy (MMH).

This study is a multicenter, randomized, double-blind, placebo-controlled, up to 2-treatment, dose escalation study. BOTOX or placebo will be administered intramuscularly to the bilateral masseter muscles (6 total injections, 3 injections/masseter). The initial BOTOX total dose will be 24 U (12 U/masseter) and the maximum BOTOX total dose will be 96 U (48 U/masseter). Stratification will be by baseline (day 1) Masseter Muscle Prominence Scale (MMPS) grade at baseline (day 1). The planned dose escalation is as follows:

Cohort	Total Dose	Sample Size	Total Subjects/Cohort
1	24 U	N=40	50
	placebo	N=10	
2	48 U	N=40	50
	placebo	N=10	
3	72 U	N=40	50
	placebo	N=10	
4	96 U	N=40	50
	placebo	N=10	

The second treatment is only allowed at the day 180 visit. Subjects will receive the same treatment as they received at the day 1 visit.

Subjects who meet the following retreatment criteria at the day 180 visit will receive a second treatment:

- Allergan written notification allowing retreatment of the current cohort

- subject has marked (grade 4) or very marked (grade 5) bilateral masseter muscle hypertrophy, as assessed by the investigator using the MMPS
- females of childbearing potential must have a negative urine pregnancy test prior to treatment

The primary efficacy variable, change from baseline in lower facial volume ( $\text{cm}^3$ , note that  $1\text{cm}^3=1\text{mL}$ ), is calculated from VECTRA M3 digital photography system 3D image models

[REDACTED]

The primary safety analysis is the calculation of incidence of treatment emergent adverse events (TEAE) for the entire study period, as well as for each treatment cycle.

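### SAP 6.5 shows the exit CT safety measures only split by retreatment status, and plans no exit summary by day 1 treatment group

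*SAP*

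**What the plan says.** CT is taken three times. Protocol 1.3 states: "Both CT and dental measures will be taken at screening (considered as baseline), day 90, and at study exit (day 360 or study discontinuation"). For subjects who leave early, Protocol 8.8 adds: "All day 360/study exit procedures should be performed (Table 1), including an exit CT scan", unless there is a medical reason to waive it.

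SAP 6.5 then fixes how the last scan is reported: "For the CT safety measurements, the exit visit will be displayed as treatment cycle 1 exit visit and treatment cycle 2 exit visit". Membership follows the number of treatments: "Only subjects who received the second injection will be included in the treatment cycle 2 exit visit", and "Subjects who received only 1 treatment will be included in the treatment cycle 1 exit visit". These sentences come at the end of the list of qualitative measures, but they refer to the CT safety measurements in general, so they cover the quantitative ones too.

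Who is retreated is set in SAP 1.1 and Protocol 5.10. The conditions are "Allergan written notification allowing retreatment of the current cohort", a negative pregnancy test where relevant, and the clinical grade: "subject has marked (grade 4) or very marked (grade 5) bilateral masseter muscle hypertrophy, as assessed by the investigator using the MMPS".

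Other safety data are handled differently. SAP 6.2 summarises treatment-emergent adverse events both by cycle and over the whole study. SAP 6.6 summarises the dental examination by visit, with no retreatment split stated. Protocol 7.1 groups safety analyses by the treatment received on day 1.

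**The concern.** The split variable is an outcome. Every subject enters at grade 4 or 5 (Protocol 4.3), so a placebo subject who does not change meets the day 180 grade criterion. A BOTOX subject whose grade is still 3 or lower at day 180 does not. If the drug works as hypothesised, the retreatment rate differs by arm. Each display then sets BOTOX subjects selected on one kind of response against placebo subjects selected on another. A difference in mandibular measures within a display could reflect that selection, or be hidden by it.

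This matters because the protocol's background section names effects on the mandible and teeth as something the study is meant to identify, and the exit scan is the only CT after day 90. It is the only planned CT view of later bone change or of bone after a second treatment.

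Timing is a second problem. The once-treated display holds day 360 scans together with scans from subjects who left at any time after day 1, so it is not a clean 12-month time point.

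**Working it through.** **The plan's own figures.** The documents give no precision, retreatment rate or dropout rate for CT. The only power figure (Protocol 7.5) is 93% for 40 against 10 within a cohort on lower facial volume, effect size 1, one-sided 0.10. A noncentral t calculation with 48 degrees of freedom gives 93.6%, so it reproduces, but it has no bearing on CT.

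**Inputs from the documents.** 40 BOTOX and 10 placebo per cohort in four planned cohorts, so 40 per dose and 4 × 10 = 40 placebo if pooled. SAP 5 states pooling for efficacy; here it is assumed for safety as well.

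**Assumed inputs.** Share retreated: *r* = 50% to 95% on placebo for the counts; 70% to 95% on placebo and 30% to 70% on BOTOX for precision. No missing exit CT.

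**Once-treated placebo subjects**, expected number 40 × (1 − r), and binomial chance of 5 or fewer:

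| r | Expected n of 40 | P(5 or fewer) |
|---|---|---|
| 95% | 2 | 99% |
| 90% | 4 | 79% |
| 80% | 8 | 16% |
| 70% | 12 | 0.9% |
| 50% | 20 | <0.01% |

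Two features raise these counts:
- If 10% leave before day 180 and 5% to 30% of the rest are below grade 4, the number is 40 × (1 − 0.90 × 0.95) = 5.8 to 40 × (1 − 0.90 × 0.70) = 14.8.
- If one cohort is not cleared for retreatment, its 10 placebo subjects all stay in the once-treated display. At r = 90% the count is then 10 + 30 × 0.10 = 13.

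**Precision**, SE of a difference in SD units = √(1/n₁ + 1/n₂):

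| Display | Placebo n | BOTOX n | SE, best to worst | Ratio to all subjects |
|---|---|---|---|---|
| All subjects at exit | 40 | 40 | √(1/40 + 1/40) = 0.22 | 1 |
| Once-treated | 2 to 12 | 12 to 28 | √(1/12 + 1/28) = 0.35 to √(1/2 + 1/12) = 0.76 | 1.5 to 3.4 |
| Retreated | 28 to 38 | 12 to 28 | √(1/38 + 1/28) = 0.25 to √(1/28 + 1/12) = 0.35 | 1.1 to 1.5 |

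A single case: with 90% of placebo and 40% of a dose group retreated, the 95% half-width (1.96 × SE) is 1.06 SD once-treated (4 against 24) and 0.59 SD retreated (36 against 16), against 0.44 SD for 40 against 40.

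These figures describe precision only. The selection problem needs no particular rate, only rates that differ by arm.

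**What a reader could rebuild.** The two displays do not overlap, and together they cover everyone with an exit CT. N, mean and SD by group can be recombined exactly, and qualitative counts add. Medians cannot be recombined, and early-exit scans cannot be separated from day 360 scans.

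**The case against.** The strongest reply is that nothing is lost. CT safety is descriptive, p-values for safety were removed by SAP Amendment 1, the day 90 comparison with placebo is not split, and most of the all-subject exit summary can be recovered from the two tables. Separating one exposure from two is also a sensible safety display in a dose-ranging phase 2 study. All of this stands, and it limits the point to a missing summary: no planned test is invalid. It does not remove the point, because the whole-group comparison should be specified in the plan and not left to reconstruction by hand.

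It may also be said that SAP 6.5 promises summaries by treatment regimen for all scheduled visits. That is the general sentence; the later text says specifically how exit is displayed.

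Three stronger readings are tempting and are not supported:
- *The 12-month comparison is never made.* The documents show only that no combined exit display is stated in the public text, parts of which are redacted, and the means can be recombined.
- *The once-treated placebo column will be nearly empty.* That needs about 90% or more of placebo retreated, few early exits and all four cohorts cleared. The documents give none of these.
- *Bone change is most to be expected in the once-treated BOTOX subjects.* Protocol 1.3 says the effect on the mandible is unknown. Retreated subjects have more exposure, and the once-treated group also includes early leavers, subjects without the required negative pregnancy test and any cohort not cleared.

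**Conclusion.** The point holds as a gap in the planned display. Under SAP 6.5 as written, the only CT after day 90 is reported in two groups defined by a day 180 outcome that treatment is meant to change, and no exit summary by day 1 treatment group is stated. Neither display compares the groups as randomised.

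The loss of precision falls mainly on the once-treated display, at 1.5 to 3.4 times the all-subject standard error under the assumed retreatment rates. The retreated display keeps substantial placebo data, at 1.1 to 1.5 times. These sizes rest on assumed retreatment rates, pooled placebo and complete exit CT. The selection argument rests only on retreatment differing by arm. Consequences are limited by the descriptive analysis and the unsplit day 90 scan, but the change is worth making because mandibular effects are a stated interest of the study.

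**What to change.** In SAP 6.5, make the main exit summary the change from screening for all subjects with an exit CT, by treatment received on day 1 and regardless of retreatment. Grouping by treatment received matches Protocol 7.1 and SAP 2.1. Keep early-exit scans in this table but identify them, and show a day 360-only version alongside. Removing early exits from the main table would itself select on a post-randomisation event.

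Keep the split by number of treatments as a supplementary table, labelled as a non-randomised comparison.

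The cost is one extra table per CT measure, from data already collected. No visit, scan or clinical procedure changes.

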## 7.7 Final Analyses

A final database lock will be performed following the last subject's completion of the day 360 (study exit or early discontinuation) visit. All study data, from every subject and every visit, will be included in this final analysis.

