## **6.5 CT Scan Safety Measures**

Using a standardized protocol, CT scans for each subject will be captured by a CT technologist at screening (baseline), treatment cycle 1 day 90, and the exit visit, and the 9 measures listed below will be assessed by a central reader.

For each of the quantitative measures, summary statistics will be presented for baseline, mean change from baseline, and percent change from baseline (sample size, mean, standard deviation, median, minimum, and maximum) by treatment regimen for all scheduled visits.

For each of the qualitative measures, the incidence of change from baseline will be summarized on a per-subject basis. Interpretation of change from baseline will be provided by the central reader in comments.

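### SAP 6.5 sorts exit CT scans only by number of treatments, so early-discontinuation scans and day-360 scans share one mean change and one incidence

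*SAP*

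**What the plan says.** Protocol 1.3 schedules CT at screening, at day 90 and "at study exit (day 360 or study discontinuation"). Protocol 8.8 states: "Subjects may voluntarily withdraw from the study at any time". It then requires of those who leave: "All day 360/study exit procedures should be performed (Table 1), including an exit CT scan", with an exception where the investigator gives a medical ground for omitting the scan. Protocol 4.5.1.1 rules out CT in pregnancy. Protocol 7.7 treats the two kinds of exit as one visit, referring to "completion of the day 360 (study exit or early discontinuation) visit".

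SAP 6.5 confirms that there is no other late scan: "CT scan is only done at screening (baseline), treatment cycle 1 day 90 and the exit visit". It then splits the exit scans in two. For retreated subjects: "Only subjects who received the second injection will be included in the treatment cycle 2 exit visit". For the rest: "Subjects who received only 1 treatment will be included in the treatment cycle 1 exit visit". Quantitative measures are summarised as baseline, change and percent change "by treatment regimen for all scheduled visits". Qualitative measures are summarised as a per-subject incidence of change.

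Retreatment at day 180 requires bilateral MMPS grade 4 or higher and the sponsor's written notification (Protocol 5.10, SAP 1.1).

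**The concern.** The assignment rule in SAP 6.5 uses one fact about a subject, the number of treatments. It uses neither the date of the exit scan nor completion status. A single-treatment subject who left on day 40 and one who completed day 360 therefore count alike in the cycle 1 exit column. The cycle 2 exit column has the same feature over a narrower range, because its subjects leave between day 180 and day 360.

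This matters because the exit scan is the only CT look after day 90. Protocol 1.3 says it is unknown whether treatment affects the mandible or dentition, and that the CT examination was designed to identify such effects. If cortical or condylar change takes months to appear, averaging early scans with late ones pulls the late result towards zero.

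The SAP is more careful about timing elsewhere. Adverse event listings give onset day relative to the most recent dose (6.2), and pregnancy listings give days since treatment (6.9). Section 6.5 specifies nothing similar.

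The mix may also differ between arms. Retreatment needs grade 4 or higher, and the efficacy responder is grade 3 or lower (SAP 5.3). If BOTOX still works at day 180, more placebo than BOTOX completers are retreated and leave the cycle 1 column, while subjects who left before day 180 stay in it in every arm.

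**Working it through.** There is no figure in the plan to reproduce here. The only design calculation (Protocol 7.5) concerns lower facial volume and has no bearing on CT.

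**Step 1, from the text.** The exit scan is at day 360 or at discontinuation (Protocol 1.3, 7.7, 8.8), and discontinuation can happen at any time (8.8). The column is decided by number of treatments alone (SAP 6.5). Hence time since injection in the cycle 1 exit column can run from shortly after day 1 to about day 360. No assumed rate is needed for this.

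**Step 2, illustration of size.** From the documents: 40 per BOTOX dose, and placebo pooled over four cohorts, 4 × 10 = 40 (SAP 1.1 and 5). Assumed, because the documents give no rates:
- a fraction d leaves before day 180, on average at day 90;
- a fraction r of those reaching day 180 is retreated;
- 5% of the non-retreated leave between days 180 and 360, on average at day 270;
- every early leaver is scanned.

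Formulas:
- non-retreated at day 180: M = 40 × (1 − d) × (1 − r)
- scans in the cycle 1 exit column: 40d + M
- early scans: 40d + 0.05M
- mean scan day: (40d × 90 + 0.05M × 270 + 0.95M × 360) / (40d + M)

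Example with d = 10%:
- r = 90%: M = 40 × 0.90 × 0.10 = 3.6. The column is 4 + 3.6 = 7.6 scans, of which 4 + 0.18 = 4.18 are early, so 4.18 / 7.6 = 55%. Mean day = (360 + 48.6 + 1231.2) / 7.6 = 216.
- r = 30%: M = 40 × 0.90 × 0.70 = 25.2. The column is 29.2 scans, of which 4 + 1.26 = 5.26 are early, so 18%. Mean day = 319.

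| d | r | Scans | Early scans | Early share | Mean scan day |
|---|---|---|---|---|---|
| 5% | 90% | 5.8 | 2.2 | 38% | 264 |
| 5% | 70% | 13.4 | 2.6 | 19% | 316 |
| 5% | 30% | 28.6 | 3.3 | 12% | 337 |
| 10% | 90% | 7.6 | 4.2 | 55% | 216 |
| 10% | 70% | 14.8 | 4.5 | 31% | 284 |
| 10% | 30% | 29.2 | 5.3 | 18% | 319 |
| 15% | 90% | 9.4 | 6.2 | 66% | 186 |
| 15% | 70% | 16.2 | 6.5 | 40% | 257 |
| 15% | 30% | 29.8 | 7.2 | 24% | 302 |

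**Step 3, what drives an arm difference.** Two arms with the same d and r sit on the same row, so the shares are equal. At equal d, the difference comes entirely from unequal r. If exit scans were shown by randomised group whatever the retreatment, and the 5% later exit applied to everyone, the early share at d = 10% would be (4 + 0.05 × 36) / 40 = 14.5% in both arms.

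**Step 4, if not every leaver is scanned.** With half of the early leavers scanned at d = 10%: r = 90% gives 2.09 / (2.09 + 3.42) = 38%, and r = 30% gives 2.63 / (2.63 + 23.94) = 10%. The shares fall, but the mixing remains.

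**The case against.** The case against has real force on several points.

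- **Not every early leaver has an exit scan.** It can be waived on medical grounds, pregnancy bars it, and SAP 3.2 lists loss to follow-up as an exit category. This stands: the Step 2 shares are upper values for each pair of rates.
- **Visit windows.** SAP 5.1 places the windows for all time points in Section 2.2, which cannot be read in the available copy. It may move some early-exit scans, for instance to day 90. So one cannot say that the SAP has no time limit, only that the assignment rule in 6.5 is stated without one.
- **Imbalance by arm.** A reader might infer that the plan necessarily mixes follow-up times unequally by arm. The documents do not support that. They give no retreatment or dropout rates, and notification may be withheld for a whole cohort, in which case neither of its arms is retreated. Any imbalance arises from splitting by retreatment; Step 3 shows it disappearing by randomised group when dropout is equal.
- **A spurious drug effect of a given size.** A reader might turn the shares into an apparent difference in bone change. That needs a non-zero drift common to both arms and a shape for its accrual, and the documents give neither.
- **Consequence.** Protocol 1.3 calls the CT measures exploratory, 6.5 is descriptive, and SAP Amendment 1 removed safety p-values. Day 90 is a separate scheduled CT time point. No test, error rate or primary result is touched.

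None of this answers Step 1: as 6.5 reads, the only late CT summary combines scans at very different times since injection.

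**Conclusion.** The point holds in a limited form. By its own wording, SAP 6.5 combines early-discontinuation and day-360 scans in each exit column, and this can dilute a late bone signal in the only CT summary after day 90. That much rests on the text alone, subject to whatever Section 2.2 provides.

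A difference by arm is probable if BOTOX lowers MMPS grade through day 180, but it is an inference. Its size cannot be derived from the documents. Under the stated assumptions, with 5-15% leaving before day 180, early scans make up about 19-66% of the column at 70-90% retreated and 12-24% at 30% retreated. The difference is nil if retreatment and dropout are equal.

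Two labels would overstate the matter. The SAP does not call this column a 12-month result. What varies within it is time since injection, not exposure, since everyone in it had one treatment. The effect is on how a descriptive safety table can be read, and the change is worth making because it is cheap.

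**What to change.** In SAP 6.5:

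1. Keep the exit summary of all subjects, so that those who discontinue stay in the safety incidence.
2. Add a summary by treatment regimen restricted to exit scans inside the day-360 window.
3. Show early-exit scans as a separate category.
4. Report days since last injection for each exit scan.
5. Where an early-exit scan falls in the day-90 window and no other day-90 scan exists, assign it to day 90, consistent with the Section 2.2 windows. Cross-refer to that section.

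Simply dropping early-exit scans from the summaries would be a worse remedy. It would take discontinuers, possibly including those leaving for adverse events, out of the incidence of bone change, and a listing would not put them back.

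The cost is one extra table and a filter on scan date; no study procedure changes. The day-360 placebo cycle 1 column may be small: at d = 10% and r = 90% it would hold 0.95 × 3.6 = 3.4 scans, and at r = 70%, 0.95 × 10.8 = 10.3. That is a reason to show it beside the all-subject summary, not in place of it.
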